## 9.0 Study Calendar

	Pre-Study (within 28 days)	Cycle 1			Cycle 2 and beyond (Each cycle 3 weeks)			Off Study Visit
		Wk 1	Wk 2 +/- 1 day	Wk3 +/- 1 day	Wk1	Wk2	Wk3	
BV		X			x			
Ibrutinib		X	X	X	x	x	x	
Informed consent	X							
Demographics	X							
Medical history	X							X
Concurrent meds	X				x			X
Physical exam	X	X			x			X
Vital signs	X	X			x			X
Height	X							
Weight	X	X			x			X
Performance Status	X	X			x			X
CBC w/diff, plts	X	X	X	X	x			X
Serum chemistry a	X	X	X	X	x			X
PT/PTT/INR	X				x			
EKG (as indicated)	X							
Adverse event evaluation		X	X	X	X			X
Tumor measurements	X				X b			
Radiologic evaluation	X				X c			
B-HCG	X							
Tissue for correlative studiesd	X							X
Peripheral blood for correlative studiese		X	X		X			

- a. Serum chemistry includes (comprehensive metabolic profile: sodium, potassium, chloride, carbon dioxide, glucose, blood urea nitrogen, creatinine, AST, ALT, Alkaline phosphate, total bilirubin, calcium, albumin, total protein, magnesium, phosphate).
- b. Tumor measurements to be done at end of C2 (+/- 7 days), C4 (+/- 7 days),, C7 (+/- 7 days),, and every 3 cycles until patients achieves CR. Once CR documented twice by CT scan, intervals can be increased to q6 cycles while patient is still on study drug. If patient comes off study, CT scan will only be performed q6 month for 2 years and no protocol scans will be done 2 years post treatment.
- c. CT/PET to be done at C4 (+/- 7 days),, C10 (+/- 7 days),, and q 6 cycles until patient achieves CR. However, once CT/PET is negative, only CT scan need to be done after that, PET can be avoided.
- d. Each subject will have either a fresh core or excisional biopsy of a tumor lesion prior to starting study therapy or will have available archival tissue from a biopsy that was performed after the most recent therapy and within 3 months of the screening date. *If feasible*, all subjects will also undergo biopsy of a tumor lesion at the time of disease progression. Refer to [Section 8](#) for details.
- e. Peripheral blood for correlative studies to be collected prior to cycle 1, day 8 of cycle 1, and day 1 of cycle 2 prior to treatment. Refer to [Section 8](#) for details.

## 10.0 Endpoint Evaluation Criteria/Measurement of Effect

---

### 10.1 Definitions

**Evaluable for toxicity:** All participants will be evaluable for toxicity from the time of their first treatment with ibrutinib plus brentuximab vedotin.

**Evaluable for objective response:** Only those participants who have measurable disease present at baseline, have received at least one cycle of therapy, and have had their disease re-evaluated will be considered evaluable for response. These participants will have their response classified according to the definitions stated below.

**Duration of overall response:** The duration of overall response is measured from the time measurement criteria are met for CR or PR, per Cheson criteria, (whichever is first recorded) until the first date that relapsed or progressive disease is objectively documented.

**Duration of overall CR:** The duration of overall CR is measured from the time measurement criteria are first met for CR until the first date that progressive disease is objectively documented.

**Duration of stable disease:** Stable disease is measured from the start of the treatment until the criteria for progression are met, per Cheson criteria, taking as reference the smallest measurements recorded since the treatment started, including the baseline measurements.

**Overall Survival (OS):** OS is defined as the duration of time from start of treatment to time of death (due to any cause).

**Progression-Free Survival (PFS):** PFS is defined as the duration of time from start of treatment to time of progression or death, whichever occurs first.

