**Sample Size:**

Assuming 1) the ibrutinib 560mg and brentuximab vedotin 1.8mg/kg doses are well tolerated and 2) the study does not close for futility, 39 evaluable (received at least one cycle of treatment) patients will be enrolled on the phase II portion of the study. Note: Expected accrual for safety lead-in segment: n=9.

Estimated Duration of the Study
In the event that the study does not close for futility, accrual is expected to be completed in 45 months; with approximately 1-2 patients enrolled each month. Patients will be treated in 21-day treatment cycles until disease relapse, progression, unacceptable toxicity, or withdrawal of consent. Patients who discontinue study treatment for reasons other than disease relapse/progression will continue to have disease assessments per Cheson criteria  until relapse or progression, initiation of new anticancer treatment, or death whichever occurs first. Patients will be followed to collect further anticancer treatment (including HCT) and survival information until death, loss to follow-up, withdrawal of consent, study termination or up to 24 months post completion/ discontinuation of treatment.
Summary of Subject Eligibility Criteria:
Inclusion Criteria:

 
1) Relapsed/refractory biopsy-proven CD30+ Hodgkin Lymphoma
 
2) Age <math>\geq</math> 15 years old and <math>> 40\text{kg}</math>
 
3) ECOG Performance status 0-2
 
4) Prior exposure to brentuximab vedotin (relapsed disease after 3 month, not refractory disease) is allowed
 
5) Prior autologous hematopoietic cell transplant is allowed
 
6) Prior allogeneic hematopoietic cell transplant (allo-HCT) is allowed, provided there is no active GVHD and the patient is not taking immunosuppressive agents. Patient has to be at least 3 months out of allo-HCT.
 
7) Prior radiation therapy is allowed.
 
8) Patients may be on steroids before initiation of treatment, provided that use was tapered down to <math>\leq 20</math> mg prednisone or equivalent by cycle 1 day 1.
 

Exclusion Criteria:

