**Analysis:** All patients who met the eligibility criteria (with the exception of those who received no study medication) will be included in the main analysis of response and survival endpoints and all of the secondary or correlative analysis described below.

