### **3.1 Inclusion Criteria**

- Patients must have histologically documented or cytologically confirmed Hodgkin lymphoma with CD30 expression.
- Patients must have ANC  $\geq 1000/\mu\text{L}$ , Plt  $\geq 50,000/\mu\text{L}$ , and hemoglobin  $\geq 8.5 \text{ g/dL}$ . Neupogen can be given before and during treatment to achieve target ANC  $\geq 1000/\mu\text{L}$ . Platelet transfusion and packed red blood cell transfusion can also be given prior to the start of treatment and during treatment to achieve a target plt  $\geq 50,000/\mu\text{L}$  and hemoglobin of  $\geq 8.5/\mu\text{L}$  provided that patients have not received growth factors for at least 14 days prior to entering trial.
- Patients must have measurable disease  $> 1.5 \text{ cm}$  evidenced by CT scan of the neck/chest/abd/pelvis or CT/PET scans.
- Patients must be either refractory to or relapsed after 1 line of therapy.
- Prior radiation therapy is allowed.
- Voluntary written informed consent before performance of any study-related procedure not part of normal medical care, with the understanding that consent may be withdrawn by the subject at any time without prejudice to future medical care.
- Female subject is either post-menopausal, surgically sterilized, or willing to use an acceptable method of birth control (i.e. a hormonal contraceptive, intra-uterine device, diaphragm with spermicide, condom with spermicide, or abstinence) for the duration of the study.
- Male subject agrees to use an acceptable method of contraception for the duration of the study.
- Age  $\geq 15$  years old and over 40 kg. Life expectancy of greater than 3 months.
- ECOG of 0-2.
- Patients must have normal organ and marrow function as defined below:
  - Total bilirubin within 1.5x the upper limit of normal institutional limits. Patients with elevation of unconjugated bilirubin alone, as in Gilbert's disease, are eligible.
  - AST/ALT  $\leq 3.0$ x institutional upper limit of normal (unless demonstrated Hodgkin lymphoma involvement of the liver). Estimated creatinine clearance  $\geq 30 \text{ ml/min}$  (Cockcroft-Gault) and/or 24 urine analysis as needed
  - PT/INR  $< 1.5 \times \text{ULN}$  and PTT (aPTT)  $< 1.5 \times \text{ULN}$ .

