#### 11.2 Sample Size Accrual Rate

Assuming 1) the ibrutinib 560 mg and brentuximab vedotin 1.8mg/kg doses are well tolerated and 2) the study does not close for futility, 39 evaluable participants (received at least 1 cycle of treatment) will be enrolled on the phase II portion of the study. Study enrollment will be complete within 24 months from activation (accrual of 1-2 participants per month). Note: Expected accrual for the safety lead-in segment: n=9.

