### 11.4 Statistical Analysis Plan

In general, data will be summarized by using counts and percents for discrete parameters, and by descriptive statistics (number of observations, mean, standard deviation, median, minimum and maximum) for continuous parameters. The complete response rate will be calculated as the percent of evaluable patients that have confirmed CR; exact 95% confidence intervals will be calculated for this estimate. Observed toxicities will be summarized in terms of type (organ affected or laboratory determination), severity, time of onset, duration, probable association with the study regimen and reversibility or outcome. Baseline information (e.g. the extent of prior therapy) and demographic information will be presented as well to describe the patients treated in this study. Time to response and survival endpoints will be estimated using the product-limit method of Kaplan and Meier. The cumulative incidence of relapse/progression and non-relapse mortality will be calculated as competing risks.

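### The Synopsis and the body of the protocol give different denominators for the primary CR rate, and the body's version drops treated patients who were never re-evaluated

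*Combined protocol and SAP*

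**What the plan says.** Three parts of the document bear on who is in the denominator of the primary endpoint.

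- **Synopsis, Analysis paragraph.** The rule reads: "All patients who met the eligibility criteria (with the exception of those who received no study medication) will be included in the main analysis". It covers both response and survival. The sentence does not require a completed cycle or a follow-up assessment, and it is not restricted to the phase II portion.
- **Section 10.1, the definition of who can be assessed for response.** The set is limited as follows: "Only those participants who have measurable disease present at baseline, have received at least one cycle of therapy, and have had their disease re-evaluated".
- **Section 11.4.** The primary estimate is set out thus: "The complete response rate will be calculated as the percent of evaluable patients that have confirmed CR". Exact 95% limits go with it. The section neither defines the word evaluable nor refers to another section for it.

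The same word has a further meaning in the accrual target. Section 11.2 says "39 evaluable participants (received at least 1 cycle of treatment) will be enrolled on the phase II portion of the study", and the Synopsis (Sample Size) says the same. No re-evaluation is required there, but these are enrolment statements, not analysis rules.

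No section says how a treated patient without a response assessment is counted, or whether such a patient is replaced.

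**The concern.** The CR rate is the primary endpoint of a single-arm trial with 39 phase II patients, so each patient removed from the denominator moves the estimate by more than one percentage point. A treated patient who is never re-evaluated cannot be a documented CR. Leaving that patient out removes a certain non-CR, so the estimate and both confidence limits can only rise.

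The same data can therefore give different primary results depending on which section the analyst follows, and the choice could be made after the data are known.

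**Working it through.** **1. Where the two sets differ.** Section 3.1 already makes measurable disease an entry criterion ("Patients must have measurable disease"). For eligible patients, the Synopsis set and the Section 10.1 set therefore differ only through the one-cycle and re-evaluation conditions. The first scheduled on-treatment tumour measurement is at the end of cycle 2 (Section 9.0, footnote b), so a completed first cycle does not guarantee a re-evaluation.

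| Treated, eligible patient | Synopsis, Analysis | Section 10.1 | Accrual wording (Section 11.2) |
|---|---|---|---|
| Leaves during cycle 1, never re-evaluated | in | out | out |
| Completes cycle 1, dies or withdraws before any re-evaluation | in | out | in |
| Less than one cycle, scanned later | in | out | out |
| At least one cycle and re-evaluated | in | in | in |

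**2. The plan's design figures reproduce.** Inputs from Section 11.1.1: 19 patients in stage 1, stop at 6 or fewer CRs; 20 more in stage 2, success at 17 or more CRs of 39; null rate 30%, target 50%, type I error 0.05, power 80%. With X1 ~ Bin(19, p) and X2 ~ Bin(20, p),

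P(success) = sum over x = 7 to 19 of P(X1 = x) × P(X2 ≥ 17 − x).

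This gives 0.0455 at p = 0.30 and 0.8036 at p = 0.50, within the stated limits.

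**3. Effect on the estimate.** Take 39 treated patients and 17 CRs, the smallest number that counts as success. The documents give no number of never-assessed patients, so one to three are assumed. Intervals are Clopper-Pearson, not adjusted for the two stages.

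| Never-assessed patients dropped | CR rate | Exact 95% CI |
|---|---|---|
| 0 | 17/39 = 43.6% | 27.8 to 60.4% |
| 1 | 17/38 = 44.7% | 28.6 to 61.7% |
| 2 | 17/37 = 45.9% | 29.5 to 63.1% |
| 3 | 17/36 = 47.2% | 30.4 to 64.5% |

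The upward direction is certain only for never-assessed patients. A patient with less than one cycle who is scanned later could in principle be a CR. Dropping one such CR gives 16/38 = 42.1% (26.3 to 59.2%), an unlikely case.

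**4. Effect on the decision.**

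- *No replacement.* The rule counts CRs among patients entered. Dropping a non-CR from the denominator leaves the count as it was, so the decision is the same. Type I error is 0.0455 if 30% is the rate among all treated patients.
- *Replacement until 39 are evaluable, with 30% as the all-treated rate.* If a fraction d of treated patients is dropped and none of them is a CR, the rate among those analysed at the null is 0.30/(1 − d). For assumed d of 2.5%, 5% and 10% this is 0.3077, 0.3158 and 0.3333, and P(success) is 5.7%, 7.1% and 10.9%.
- *Replacement, with 30% as the rate among evaluable patients.* P(success) at the null stays 0.0455 for any d.

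**The case against.** **Section 11.4 is not silent.** It uses the word evaluable, and Section 10.1 is the only place that defines the word for response. The ordinary reading is that 11.4 means the 10.1 set. This stands, and it makes the problem narrower: the body (10.1 with 11.4) contradicts the Synopsis. It does not remove the problem, because the Synopsis sentence expressly governs the main analysis of response.

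**Few patients would be dropped.** The Synopsis says "Patients who discontinue study treatment for reasons other than disease relapse/progression will continue to have disease assessments"; Section 5.2 expects at least four cycles unless there is progression or intolerable toxicity; Section 3.1 requires a life expectancy above three months. Section 10.1 asks for a re-evaluation, not specifically the end-of-cycle-2 scan, so documented early progression arguably qualifies. What remains is mainly early death or withdrawal. This also stands: shifts of one to four points are small beside an interval about 33 points wide. It limits the size, not the direction.

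**Type I error.** A reader might infer from the evaluable-patient wording that the trial's type I error exceeds 5%. The documents do not support that. The inflated figures need three things together: replacement, 30% meant as an all-treated rate, and a non-trivial drop rate. None is stated. The accrual target of 39 evaluable patients hints at replacement, but Section 11.1.1 sets its rules on patients entered and expects a maximum of 39.

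**Choice of primary set.** The documents need only name one set; preferring all treated patients is a judgement. It is, however, the Synopsis's own rule and the one that does not discard known non-CRs.

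**Conclusion.** The conflict is real and should be fixed. The demonstrated harm is to the reported CR rate and its interval: with 17 CRs, about 1.1, 2.3 or 3.6 percentage points upward for one, two or three never-assessed patients dropped. Those counts are assumptions and the true number is probably low.

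The go/no-go decision is not shown to be affected. It changes only if dropped patients are replaced; the type I figures of 5.7%, 7.1% and 10.9% are a conditional sensitivity, not an error found in the plan. Likewise, a reader might infer that the lower limit passing 30% when three patients are dropped would turn a failed trial into a success. It would not: success depends on the count of 17 CRs, and the interval plays no part in the rule.

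**What to change.** - In the Synopsis (Analysis) and Sections 10.1 and 11.4, name one primary response set: all eligible phase II patients who received any study drug. Bring the word evaluable in the Synopsis (Sample Size) and Section 11.2 into line with it, and align the references to 39 patients evaluated for response in the Synopsis (Study Design) and Sections 5.1.7 and 11.1.2.
- Count a patient with no post-baseline assessment as not CR.
- State that the 19 and 39 in the 6/19 and 16/39 rules count eligible treated phase II patients. Entrants who prove ineligible or are never dosed (Section 4.1.5 foresees registered patients who do not start) then do not use up a place, and treated but unassessed patients are not replaced. This matters: with the thresholds kept and one place lost, power at 50% falls from 80.4% to 77.0% if the loss is in stage 2, or 75.2% if in stage 1.
- State in the Synopsis (Statistical Considerations) and Section 11.1.1 that 30% and 50% are rates among treated patients; type I error 0.0455 and power 0.8036 then hold. If rates among evaluable patients were meant, say so and restate power. Counting the unassessed as non-CR makes the success probabilities those at 0.50(1 − d) and 0.30(1 − d): power 75.9%, 71.0% or 59.9% and type I error 3.6%, 2.9% or 1.7% at an assumed 2.5%, 5% or 10% unassessed.
- Report the Section 10.1 subset as a labelled sensitivity analysis.

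The cost is wording changes and a possibly slightly lower reported CR rate. The two-stage boundaries, treatment and visit schedule are unchanged.

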### 10.2 Transplant Endpoint Definitions

**Overall Survival (OS):** OS is defined as the duration of time from start of HCT treatment to time of death (due to any cause). Evaluated and recorded at day 30, day 100, 6 months, 1-year and 2-years post HCT.

**Progression-Free Survival (PFS):** PFS is defined as the duration of time from start of HCT treatment to time of progression or death, whichever occurs first. Evaluated and recorded at day 30, day 100, 6 months, 1-year and 2-years post HCT.

**Relapse/Progression (CIR):** The event is relapse/progression. The time to this event is measured from start of HCT treatment. Deaths without relapse/progression are considered a competing risk. Surviving patients with no history of relapse/progression are censored at time of last follow-up. Evaluated and recorded at day 30, day 100, 6 months, 1-year and 2-years post HCT.

**Non-relapse mortality (NRM):** NRM is defined as death occurring in a patient from causes other than relapse or progression. NRM is measured from start of treatment until non-disease related death, or last follow-up, whichever comes first. Deaths from relapse/progression are considered a competing risk. Evaluated and recorded at day 30, day 100, 6 months, 1-year and 2-years post HCT.

**Stem cell mobilization:** mobilization regimen used, median number of cells collected, median number of days to reach minimum collection.

**Engraftment (Recovery of Granulopoiesis and Megakaryopoiesis):** Engraftment will be assessed using three distinct milestones: 1) (Autologous and Allogeneic) ANC (neutrophils)  $\geq 0.5 \times 10^3/\mu\text{L}$  achieved and sustained for 3 consecutive lab values on different days with no subsequent decline; 2) (Autologous) Platelets (PLT)  $\geq 20 \text{ K}/\mu\text{L}$  independent of platelet transfusion support; and 3) (Allogeneic) PLT  $\geq 25 \text{ K}/\mu\text{L}$

independent of platelet transfusion support. For platelet recovery, date should reflect no transfusions in previous 3 days and the first of 3 consecutive lab values on different days.

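### Section 10.2 times transplant NRM from start of treatment but transplant OS, PFS and relapse from start of HCT, so NRM conflicts with its own post-HCT landmarks and does not share a time axis with relapse

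*Combined protocol and SAP*

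**What the plan says.** Section 10.2 (Transplant Endpoint Definitions) gives four time-to-event endpoints for patients who go on to HCT. Three share an origin. PFS reads "PFS is defined as the duration of time from start of HCT treatment to time of progression or death, whichever occurs first", OS has the same origin, and for relapse/progression "The time to this event is measured from start of HCT treatment".

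NRM is worded differently: "NRM is measured from start of treatment until non-disease related death, or last follow-up, whichever comes first". Its competing event is death from relapse or progression.

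All four definitions close with the same sentence: "Evaluated and recorded at day 30, day 100, 6 months, 1-year and 2-years post HCT".

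Section 10.1 defines the non-transplant endpoints with the phrase that NRM carries; there, "PFS is defined as the duration of time from start of treatment to time of progression or death, whichever occurs first". In 10.1 this is the study-therapy clock.

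Section 11.4 then plans the two transplant incidences together: "The cumulative incidence of relapse/progression and non-relapse mortality will be calculated as competing risks".

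**The concern.** Section 10 uses two phrases for two clocks. The transplant endpoints add HCT to the origin and the study endpoints do not. NRM is a transplant endpoint that carries the study-therapy phrase.

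Two consequences follow if the sentence is implemented as it stands:

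- **Guaranteed event-free time.** A transplanted patient is by definition alive until HCT. Counting from study therapy adds a stretch in which NRM cannot occur, which pulls early NRM towards zero.
- **No common axis.** Cumulative incidences of relapse and NRM can be set beside each other, and beside PFS, only if all start at the same moment.

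Describing outcomes after autologous or allogeneic HCT is a stated secondary objective (section 1.0), and early NRM is one of the outcomes defined for it.

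**Working it through.** The documents give no NRM figure, so there is nothing to reproduce. The check compares the definitions and then works out what each reading implies.

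**Inputs**
- Cycle length: 21 days (5.2).
- Minimum before discontinuation: 4 cycles, except for progressive disease or intolerable AEs (5.2).
- Permitted delay of the next cycle: up to 3 weeks, i.e. 21 days (6.2).
- Landmarks: day 30, day 100, 6 months, 1 year and 2 years, all post HCT (10.2).

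**Reading A: landmarks also taken on the study-treatment clock**

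Post-HCT days covered = max(0, landmark − (cycles × 21 + delay)), with HCT assumed to start as soon as the last cycle ends. For day 100:

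| Treatment before HCT | Days elapsed at HCT | Post-HCT days within day 100 |
|---|---|---|
| 1 cycle | 21 | 79 |
| 2 cycles | 42 | 58 |
| 3 cycles | 63 | 37 |
| 4 cycles | 84 | 16 |
| 4 cycles + one 3-week delay | 105 | 0 |
| 5 cycles | 105 | 0 |

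The rows for 1 to 3 cycles arise only under the exceptions in 5.2. If four cycles are counted as complete at the fourth BV dose (63 days elapsed), the figure is 100 − 63 = 37. After four on-schedule cycles the other landmarks cover:
- day 30: 0 days
- 6 months: 182 − 84 = 98 days
- 1 year: 365 − 84 = 281 days
- 2 years: 730 − 84 = 646 days

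**Reading B: landmarks as written, post HCT**

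Day 100 post HCT falls at study day 84 + 100 = 184 after four cycles and 105 + 100 = 205 after five. On the study clock it is a different time for each patient, so one NRM curve with that origin cannot be read at it. Nothing is necessarily undercounted on this reading, but the origin and the landmark contradict each other.

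**Effect on the competing-risks pair (illustration)**

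Assumed constant post-HCT hazards, not taken from the documents: relapse 0.03 per month, NRM 0.01 per month. The cumulative incidence for cause k is λₖ/0.04 × (1 − exp(−0.04t)), and PFS is exp(−0.04t), with t in months of 30.4375 days. HCT is 84 days after study start, and NRM follows reading A.

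At day 100, t = 3.285, so CIR = 0.092 and PFS = 0.877. NRM is 0.0308 when timed from HCT. On the study clock only 16 days count (t = 0.526), so NRM = 0.0052.

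| Landmark | NRM from HCT | NRM on study clock | CIR + NRM + PFS, one origin | CIR + NRM + PFS, mixed origins |
|---|---|---|---|---|
| Day 100 | 0.0308 | 0.0052 | 1.000 | 0.974 |
| 6 months | 0.0533 | 0.0304 | 1.000 | 0.977 |
| 1 year | 0.0953 | 0.0772 | 1.000 | 0.982 |
| 2 years | 0.1543 | 0.1431 | 1.000 | 0.989 |

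**Competing event**

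The sums of 1.000 also assume that relapse ends the risk of NRM. Section 10.2 does not say this: CIR takes relapse/progression as its event, while NRM names only death from it as competing. A patient who relapses after HCT and later dies of another cause would count in both CIR and NRM, and the sum could then exceed 1. Section 5.2 lets patients who relapse after transplant re-enter the study, so such deaths are possible.

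**The case against.** The best answer is that a word was dropped. The definition stands under the transplant heading, follows three definitions timed from HCT, and ends with post-HCT landmarks. A statistician told to record NRM at day 100 after HCT has little reason to start the clock at cycle 1. This is a fair account of what was probably meant, and it points to the correction. It does not remove the conflict: the neighbouring definitions do include HCT, and the phrase without it has a settled meaning in 10.1.

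A reader might infer that day-100 NRM would cover at most 16 post-transplant days. The documents do not support that as a general statement. The landmark sentence places day 100 after HCT, so the figure arises only if the landmarks too are moved to the study clock. Even then 16 is not a ceiling, because the four-cycle minimum in 5.2 has exceptions. The same applies to 646 days for the 2-year landmark.

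A reader might also infer that correcting the origin alone makes PFS equal 1 − CIR − NRM. It does not, because the competing event for NRM must be aligned as well.

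Finally, the endpoint is secondary and descriptive, applies only to patients who reach HCT, and has no hypothesis, threshold or stopping rule attached. That stands and limits the severity.

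**Conclusion.** The inconsistency is real. As worded, NRM has a different time origin from the other three transplant endpoints, contradicts its own landmarks, and does not form a coherent competing-risks pair with CIR.

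The size depends on the reading. With origin and landmarks both on the study clock, day-100 NRM covers 16 post-HCT days after four on-schedule cycles, 0 after five or more, and 37 to 79 after three to one. In the illustration, day-100 NRM falls from 0.031 to 0.005; those values rest on assumed hazards and on HCT at day 84. With landmarks as written, the defect is a contradiction that the analyst must settle by guesswork.

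The severity is modest. The primary CR test, the two-stage boundaries and the sample size do not depend on this definition. It should be settled before any transplant outcome is analysed.

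**What to change.** Make three changes in section 10.2:

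1. In the NRM sentence, insert HCT before treatment, so that NRM has the same origin as transplant OS, PFS and CIR.
2. State that one recorded HCT start date is used for all four endpoints.
3. Name relapse/progression itself, not only death from it, as the competing event for NRM. CIR, NRM and PFS then sum to 1 at every landmark.

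The cost is a few words and no new data. Relapse dates are already needed for CIR, and Table 12.3.1 already schedules a transplant intake form after stem cell infusion. Sample size and the primary analysis do not change.

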## 5.2 Planned Duration of Therapy

BV will be given intravenously once every 3 weeks, ibrutinib will be given daily. Each cycle is 21 days. Patients will be treated until disease progression, unacceptable toxicity, or moving onto autologous or allogeneic-HCT. The minimum number of cycles required prior to discontinuation should be 4, unless the patient developed progressive disease or intolerable AEs. For patients who achieve CR/PR and then relapse while off treatment (for toxicities, auto-HCT, or allo-HCT), they can receive additional cycles of treatment. There will be no maximum cycles of treatment for patients at retreatment. There is no limit on the number of times patients can be retreated. For patients who ultimately undergo autologous or allogeneic-HCT and then relapse post transplant, these patients will be allowed to re-enter the study.

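### Section 10.2 defines transplant NRM by cause of death, so a non-disease death after relapse counts in both NRM and the relapse incidence that Section 11.4 pairs with it

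*Combined protocol and SAP*

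**What the plan says.** Section 10.2 (Transplant Endpoint Definitions) sets out four time-to-event endpoints after transplant, each recorded at day 30, day 100, 6 months, 1 year and 2 years.

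- **PFS:** "PFS is defined as the duration of time from start of HCT treatment to time of progression or death, whichever occurs first".
- **CIR:** the event is relapse/progression. On what competes: "Deaths without relapse/progression are considered a competing risk".
- **NRM:** "NRM is defined as death occurring in a patient from causes other than relapse or progression". On its time span: "NRM is measured from start of treatment until non-disease related death, or last follow-up, whichever comes first". On what competes: "Deaths from relapse/progression are considered a competing risk".
- **OS:** time from HCT to death from any cause.

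Section 11.4 then states the analysis: "The cumulative incidence of relapse/progression and non-relapse mortality will be calculated as competing risks".

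Two other sections bear on what happens after relapse. Section 5.2 says: "For patients who ultimately undergo autologous or allogeneic-HCT and then relapse post transplant, these patients will be allowed to re-enter the study". Section 5.4 follows transplanted patients for up to two years after HCT.

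**The concern.** Two cumulative incidences analysed as competing risks must come from mutually exclusive events. Here CIR is a first-event quantity: a patient has either relapsed or died without relapsing. NRM is classified by cause of death whenever the death occurs, and relapse does not remove the patient from follow-up for it. The definitions do not pair, and the patient who relapses and then dies of something else falls into both.

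Describing the outcomes of transplanted patients is a secondary objective in Section 1.0. A reader of those results will expect CIR plus NRM to equal one minus PFS. If such a death occurs, that will not hold, and NRM will be larger than the quantity CIR treats as its competing event. A death from another cause during re-treatment after relapse could also enter transplant NRM, depending on how its cause is assigned. Section 10.2 gives no rule for that, and in a small group the choice should not be left until the data are seen.

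**Working it through.** **Classification under Section 10.2.** The plan states no NRM or CIR figure, so there is none to reproduce. Each patient path is classified under the written rules:

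| Path after HCT | PFS event | CIR event | NRM as written | NRM on first events |
|---|---|---|---|---|
| Alive, no relapse | no | no | no | no |
| Death without relapse | yes | no | yes | yes |
| Relapse, then alive or disease death | yes | yes | no | no |
| Relapse, then death from another cause | yes | yes | **yes** | no |

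Only the last path differs. The plan allows it to be observed, because patients who relapse after HCT may re-enter and follow-up runs to two years. Whether it will occur cannot be known from the documents.

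**Count example** (counts assumed, complete follow-up). Of 20 transplanted, 8 relapse, 2 die without relapse, and 1 of the 8 later dies of another cause.

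- PFS = (20 − 8 − 2)/20 = 50%
- CIR = 8/20 = 40%
- NRM on first events = 2/20 = 10%; sum 50 + 40 + 10 = 100%
- NRM as written = (2 + 1)/20 = 15%; sum 50 + 40 + 15 = 105%

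**Hazard model** (all inputs assumed). Hazards are constant and T = 24 months, with no censoring. Net relapse at 24 months is 40% and net NRM 12%.

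- Relapse hazard: λr = −ln(0.60)/24 = 0.02128 per month
- Other-cause death hazard: λn = −ln(0.88)/24 = 0.00533 per month
- PFS = exp(−(λr + λn)T) = 0.5280
- CIR = (1 − 0.5280) × λr/(λr + λn) = 0.3775
- First-event NRM = (1 − 0.5280) × λn/(λr + λn) = 0.0945; the three sum to 1

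NRM as written adds the probability e of relapse followed by other-cause death before T:

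e = ∫₀ᵀ λr·exp(−(λr + λn)s)·(kλn/h)·(1 − exp(−h(T − s))) ds, with h = kλn + d.

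Here k is the ratio of the other-cause hazard after relapse to that before it, and d is the monthly disease-death hazard after relapse. The chance of at least one such death among n transplants is 1 − (1 − e)ⁿ, and the expected number is n·e. The number transplanted, 10 to 20, is also assumed.

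Base case, k = 1:

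| d | e (points) | n·e, n = 10 | n·e, n = 20 | P(≥1), n = 10 | P(≥1), n = 20 |
|---|---|---|---|---|---|
| 0 | 2.55 | 0.26 | 0.51 | 0.228 | 0.404 |
| 0.02 | 2.18 | 0.22 | 0.44 | 0.198 | 0.356 |
| 0.06 | 1.65 | 0.16 | 0.33 | 0.153 | 0.282 |

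Two-year NRM as written is therefore 11.1% to 12.0%, against 9.4% on first events. The excess builds with time: about 0.06 points at day 100, 0.17 to 0.19 at 6 months, and 0.57 to 0.72 at 1 year.

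Range of P(≥1) over d from 0 to 0.06 and n = 10 or 20:

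| Change from base case | P(≥1) |
|---|---|
| No other-cause death after relapse (k = 0) | 0 |
| k = 0.5 | 8% to 23% |
| k = 2 | 28% to 63% |
| Net NRM 5% | 7% to 20% |
| Net NRM 20% | 24% to 58% |

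With net relapse of 20% or 60% instead of 40%, the two-year excess is 0.79 to 1.22 or 2.59 to 4.07 points.

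**Time origin.** CIR states: "The time to this event is measured from start of HCT treatment". OS and PFS use the same origin. The NRM sentence leaves out the reference to HCT. Its time points are post HCT, so this is probably a dropped word.

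**The case against.** The best counter-argument is that Section 11.4 already settles the matter. Calculating relapse and NRM as competing risks ordinarily means a first-event analysis, in which a relapsed patient cannot later become an NRM event. Section 10.2 names one competing event for NRM without saying it is the only one, so the fault could be called incomplete wording. This does not hold up. A patient who has not relapsed or progressed cannot die from relapse/progression, so naming that death as the competing event has meaning only if relapsed patients stay at risk for NRM. A first-event reading of Section 11.4 contradicts Section 10.2, and the analyst is left to choose.

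It is also fair to say that cause-specific mortality with disease death competing is a coherent endpoint by itself, and that no section promises to add PFS, CIR and NRM. Both points are true. The fault lies in pairing that endpoint with CIR.

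The objections on size stand. Every rate is assumed. The upper ends of the probability ranges use d = 0, meaning no disease death after post-transplant relapse, which is hard to credit. With d = 0.06 and n = 20, the upper figures of 40% (base case), 58% (net NRM 20%) and 63% (k = 2) fall to 28%, 42% and 48%. With 10 to 20 patients, the sampling uncertainty in NRM would far exceed the expected excess. No hypothesis or decision depends on NRM.

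**Conclusion.** The concern holds. Applied as written, Section 10.2 counts a non-disease death after relapse in both NRM and CIR, while Section 11.4 requires the two to be mutually exclusive. That conclusion follows from the text and needs no model.

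The practical effect is conditional and modest. Under the assumed base case, 60% to 85% of trials with 10 to 20 transplants would have no such death and the same NRM under either definition. Where one occurs, crude NRM moves by 1/20 = 5 points or 1/10 = 10 points. Because only descriptive transplant outcomes are touched, this is a change that should be made but does not threaten the trial's main conclusion. The time-origin wording is a secondary point to correct in the same edit.

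**What to change.** Reword the NRM entry in Section 10.2 so that it pairs with CIR and with Section 11.4, for example:

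> NRM: death without prior relapse/progression, timed from the start of HCT treatment. Relapse/progression is the competing event. Patients alive and free of relapse/progression are censored at last follow-up.

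List non-disease deaths after relapse separately, by cause, so that they are still reported.

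The cost is one reworded definition and one extra line in the report. No new data are needed, because the relapse and death dates are already required for transplant PFS, OS and CIR. With this wording, CIR plus NRM equals one minus PFS however many non-disease deaths follow relapse.
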